##### Drugs that are potent CYP3A4/5 inducers

As it is with other medications that are metabolized by CYP3A4, clinical judgment is to be exercised when potent CYP3A4 inducers are concomitantly taken with panobinostat.

## Serum Electrolytes

Any patients who are taking medications that have the potential to alter serum electrolytes (e.g. diuretics) should be monitored closely for electrolyte abnormalities as these can contribute to the risk of QTc prolongation and ventricular arrhythmias.

## Anti-Coagulant Therapy

Panobinostat therapy is commonly associated with mild to moderate degree thrombocytopenia, which may increase the risk of bleeding with concomitant sodium warfarin (Coumadin). It is recommended that patients who require anticoagulation therapy while on panobinostat therapy use low molecular weight heparin (LMWH). However, if the use of LMWH is not feasible, patients on sodium warfarin may continue such therapy while on panobinostat but for such patients, PT/INR should be closely monitored and maintained within a therapeutic range. The dose of sodium warfarin may be adjusted as needed while on panobinostat. If the patient's platelets drop below 50,000 consideration should be given to suspending treatment with anticoagulation.

## **8.2. Carfilzomib**

### **8.2.1. Carfilzomib Formulation**

Carfilzomib for injection will be provided as a lyophilized powder which, when reconstituted, contains 2 mg/mL isotonic solution of carfilzomib free base in 10 mM sodium citrate buffer (pH 3.5) containing 10% (w/v) sulfobutylether- $\beta$ -cyclodextrin (SBE- $\beta$ -CD, Captisol®).

### **8.2.2. Drug Supply of Carfilzomib**

Carfilzomib for use in this study will be supplied to the Sponsor, SCRI Innovations by Onyx. Study sites will obtain carfilzomib from Sponsor designee(s) at SCRI Innovations per instructions provided to participating study sites.

Accountability for the drug at all study sites is the responsibility of the principal investigator at each study site. The investigator will ensure that the drug is used only in accordance with this protocol. Drug accountability records indicating the drug's delivery date to the site (if applicable), inventory at the site (if applicable), use by each patient, and return to SCRI Innovations or disposal of the drug (if applicable and if approved by SCRI Innovations) will be maintained by the clinical site. Accountability records will include dates, quantities, lot numbers, expiration dates (if applicable), and patient numbers. Once carfilzomib is shipped to a site, it may not be shipped or shared with another site or patient.

All material containing carfilzomib will be treated and disposed of as hazardous waste in accordance with governing regulations.

### 8.2.3. Storage and Stability

Lyophilized carfilzomib for injection must be stored at 2–8°C, in a securely locked area to which access is limited to appropriate study personnel.

### 8.2.4. Administration

Carfilzomib for Injection is supplied as a lyophilized parenteral product in single-use vials. The lyophilized product is reconstituted with water for injection to a final carfilzomib concentration of 2.0 mg/mL prior to administration. The dose will be calculated using the subject's actual BSA at baseline. Subjects with a BSA > 2.2 m^2 will receive a dose based upon a 2.2 m^2 BSA.

At least 48 hours before Cycle 1 Day 1, **oral hydration** should be given as follows: 30 mL/kg/day (approximately 6 to 8 cups of liquid per day) continuing up to the time of treatment. Subject compliance must be assessed before initiating treatment, which is to be delayed if oral hydration is not adequate. In subjects considered at risk for TLS, oral hydration should be continued in Cycle 2 and beyond as required by the subject's medical condition and at the Investigator's discretion.

**IV hydration** will be given immediately prior to carfilzomib during Cycle 1. This will consist of 250 to 500 mL normal saline or other appropriate IV fluid. If lactate dehydrogenase (LDH) or uric acid is elevated (and/or in subjects considered still at risk for TLS) at Cycle 2 Day 1, then the recommended IV hydration should be given additionally before each dose in Cycle 2. The goal of the hydration program is to maintain robust urine output (e.g., ≥ 2 L/day). Subjects should be monitored periodically during this period for evidence of fluid overload.

If the subject has a dedicated line for carfilzomib administration, the line must be flushed with a minimum of 20 mL of normal saline prior to and after drug administration.

Carfilzomib will be given as an IV infusion over approximately 10 minutes. For doses > 27 mg/m^2, carfilzomib should be infused over 30 minutes. The dose will be administered at a facility capable of managing hypersensitivity reactions. Subjects will remain at the clinic under observation for at least 1 hour following each dose of carfilzomib in Cycle 1 and following the dose on Cycle 2 Day 1. During these observation times, **post dose IV hydration** (between 250 mL and 500 mL normal saline or other appropriate IV fluid formulation) will be given. Subjects should be monitored periodically during this period for evidence of fluid overload.

### 8.2.5. Carfilzomib Toxicities

Most frequently reported adverse events are reported in the current carfilzomib Investigator's Brochure (IB).

### 8.2.6. Carfilzomib Precautions and Risks

The precautions and risks that are related to carfilzomib are pulmonary hypertension, cardiopulmonary disorders, acute renal failure, tumor lysis syndrome, infusion reactions,

thrombocytopenia, hepatic toxicity, thrombocytopenic thrombotic purpura/hemolytic uremic syndrome (TTP/HUS), and posterior reversible encephalopathy syndrome (PRES). Management of carfilzomib-related toxicities is addressed in Section 6.3 and 6.4 and in the current carfilzomib IB.

## 9. RESPONSE EVALUATIONS AND MEASUREMENTS

Response to treatment and disease progression will be evaluated using the International Myeloma Working group Uniform Response Criteria: Disease Progression and Relapse (see Appendix C).

CR	Complete Response
sCR	subcategory: stringent complete response
VGPR	Very good partial response
PR	Partial response
SD	Stable disease
PD	Progressive disease

All response categories (CR, sCR, VGPR, PR, PD) require two consecutive assessments made at any time before the institution of any new therapy, as well as no known evidence of progressive or new bone lesions if radiographic studies were performed. Radiographic studies are not required to satisfy these response requirements. Bone marrow assessments are not required to be confirmed by repeat testing.

Complete Response should be confirmed with a bone marrow biopsy for morphology and a bone marrow aspiration for flow cytometry, FISH and cytogenetics performed locally. Additional confirmatory studies include SPEP, UPEP, immunofixation of blood and urine and serum free light chains (see Appendix E).

MR	Minimal Response
-----------	------------------

Minimal Response (MR) should be reported for patients with relapsed refractory myeloma. When reported, the specific rate of MR should be distinguished from PR or better.

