#### **10.4.2. Secondary Efficacy Endpoint(s)**

Time-to-progression (TTP), progression-free survival (PFS) and overall survival (OS) will be analyzed using Kaplan-Meier methods. Time-to-progression will be measured from the date of first protocol treatment until the date of tumor progression is documented (event), or date of last adequate tumor assessment (censored). Progression-free survival will be measured from the date of first protocol treatment until the date of tumor progression is documented or death occurs (event), or date of last adequate tumor assessment (censored). Overall survival will be measured as the interval from first study treatment until date of death (event), or date last known alive (censored). Median progression-free survival and median overall survival will be reported using the respective point estimate and 95% confidence intervals.

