PDc Progressive Disease	
Increase of <math>\geq 25\%</math> from the nadir in at least one of the following criteria:
 
 
• serum M-protein (absolute increase must be <math>\geq 0.5</math> g/dL)
 
• urine M-protein (absolute increase must be <math>\geq 200</math> mg/24h)
 
• only in patients with non-measurable serum and urine M-protein levels: difference in involved and uninvolved FLC levels (absolute increase must be <math>>10</math> mg/dL)
 
• only in patients with non-measurable serum and urine M-protein levels and non-measurable disease by FLC levels, bone marrow plasma cell percentage (absolute % must be <math>\geq 10\%</math>)
 
 
OR
 
 
• definite development of new lytic bone lesions or increase from baseline in size of lytic bone lesion(s)
 
 
OR
 
 
• development of new soft tissue plasmacytoma(s) or definite increase from nadir in existing soft tissue plasmacytomas
 
 
OR
 
 
• development of hypercalcemia (corrected serum calcium <math>>11.5</math> mg/dL) for patients without hypercalcemia at baseline. In case of preexisting hypercalcemia at baseline, PD will only be assessed due to the hypercalcemia criterion in case the corrected serum calcium level was <math>\leq 11.5</math> mg/dL post-baseline and increased thereafter beyond 11.5 mg/dL.
 

Patients with relapsed refractory myeloma (adopted from the European Group for Blood and Marrow Transplantation [EBMT] criteria)	
MR Minimal Response	
 
• <math>\geq 25\%</math> but <math>\leq 49\%</math> reduction of serum M protein and reduction in 24-hour urine M-protein by 50-89%
 
 
AND
 
 
• If present at baseline, 25-49% reduction in the size of soft tissue plasmacytomas is also required
 
• No increase in size or number of lytic bone lesions (development of compression fracture does not exclude response)
 

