aAll response categories require two consecutive assessments made at any time before the institution of any new therapy; all categories also require no known evidence of progressive or new bone lesions if radiographic studies were performed. Radiographic studies are not required to satisfy these response requirements.

bConfirmation with repeat bone marrow biopsy not needed.

cAt any point in this treatment, patients suspected of PD will have response assessed again to confirm disease progression (i.e. 2 sets of response assessments at least 1 week apart). The outcomes will be reviewed by the study chair before the patient is removed from the study

Rajkumar et al. Consensus recommendations for the uniform reporting of clinical trials: report of the International Myeloma Workshop Consensus Panel 1. Blood J 2011 117: 4691-4695

Blade J, Samson D, Reece D, et al. Criteria for evaluating disease response and progression in patients with multiple myeloma treated by high dose therapy and haemopoietic stem cell transplantation:

Myeloma Subcommittee of the EBMT, European Group for Blood and Marrow Transplant. *Br J Haematol.* 1998;102(5):1115-1123.

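### Section 9 and Appendix C footnote a contradict the Appendix C definition of PD on bone lesions, so the same patient can be scored three ways for TTP and PFS

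*Combined protocol and SAP*

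**What the plan says.** Section 9 sends the assessor to Appendix C (headed Appendix 3 in the appendices) for progression as well as response: "Response to treatment and disease progression will be evaluated using the International Myeloma Working group Uniform Response Criteria". It then gives a confirmation rule, "All response categories (CR, sCR, VGPR, PR, PD) require two consecutive assessments made at any time before the institution of any new therapy", and the same sentence continues "as well as no known evidence of progressive or new bone lesions if radiographic studies were performed". PD is in the bracketed list; SD is not.

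In Appendix C, footnote a is attached to the table title and says that "all categories also require no known evidence of progressive or new bone lesions if radiographic studies were performed". The PD row offers several criteria joined by OR, one of which is "definite development of new lytic bone lesions or increase from baseline in size of lytic bone lesion(s"). Footnote c, attached to PD, says that "patients suspected of PD will have response assessed again to confirm disease progression". It carries no bone-lesion condition. Section 7.4 asks for the same repeat assessment with study chair review, and dates progression to the first of the two sets.

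Section 10.4.2 makes documented progression the event for TTP, and progression or death the event for PFS. A patient without an event is censored: "or date of last adequate tumor assessment (censored").

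**The concern.** A condition that no bone lesion has progressed is sensible for a response: a falling M-protein should not count as PR if the skeleton is getting worse. Attached to PD, the same condition works backwards. Of two patients with the same M-protein rise, the one who also has new lytic lesions is the one who fails the rule.

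Progression supplies the events for TTP and most of the purpose of PFS. If the general condition is applied, a patient leaves the event count because of the progression itself, and the Kaplan-Meier curve sits too high. If some sites apply it and others follow the PD row, progression dates are not comparable within one multicentre trial. Section 5 also ties continuation of treatment to the same classification, which is a further reason why the passages must be reconciled.

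**Working it through.** The plan states no figure on this point, so there is none to reproduce. The check is a comparison of texts, followed by an illustration of size.

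**Step 1: apply each text to three records.** The M-protein example is a rise of 60% and 0.8 g/dL on two assessments, which passes the PD thresholds in Appendix C (25% and 0.5 g/dL).

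| Record | PD row | Section 9, literally | Footnote a, literally |
|---|---|---|---|
| 1. M-protein rise, no imaging | PD | PD | PD |
| 2. Same rise, plus new lytic lesions on a survey done for bone pain | PD | not PD; SD by default | no category |
| 3. Stable M-protein, new lytic lesions on such a survey | PD | not PD; SD by default | no category |

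SD arises by default under Section 9 because the SD row is a remainder category (whatever meets none of the others) and Section 9 leaves SD off its list. Footnote a reaches SD too, so nothing is left. No passage ranks the three texts.

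**Step 2: who can be affected.** The clause operates only where imaging was done. Section 7.4 includes no skeletal imaging at restaging, and note N to the schedule of assessments asks for a repeat survey only when clinically indicated, with bone pain as the example. Records 2 and 3 therefore arise only among patients imaged after baseline.

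**Step 3: size, as an illustration.**

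- Median TTP m = 5.1 months, from the earlier single-agent carfilzomib study described in Section 1.3.1. It is borrowed for scale only.
- Share f of progressions lost because bone lesions are known: not given in the documents. Assumed 0% to 30%.
- Assumptions: exponential times; the lost progressions are a random share, each censored at the time it would have counted.

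The true hazard is ln 2 / m = 0.693 / 5.1 = 0.136 per month. With a share f recoded as censored, the hazard that Kaplan-Meier sees is (1 − f) × 0.136, so the apparent median is m / (1 − f):

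| f | Calculation | Apparent median (months) | Change |
|---|---|---|---|
| 0% (PD row followed) | 5.1 / 1.0 | 5.1 | none |
| 10% | 5.1 / 0.9 | 5.7 | +11% |
| 20% | 5.1 / 0.8 | 6.4 | +25% |
| 30% | 5.1 / 0.7 | 7.3 | +43% |

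This is a worst case in that assessors always apply the general condition and no affected progression is ever counted. For PFS the shift would be smaller, because a later death can still count as an event; the documents give no input from which to compute it.

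**Step 4: what is untouched.** The primary endpoint in Section 10.4.1 counts CR, VGPR and PR, for which the clause is appropriate. The sample size in Section 10.1 uses only response rates (18% and 36%).

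**The case against.** A reader might infer that patients with new lytic lesions cannot be scored as progressed at all, and that reported TTP and PFS will be too long. The documents do not support that.

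- Section 9 itself refers to Appendix C for progression, and the PD row there makes bone lesions sufficient. Footnote c and Section 7.4 describe how PD is confirmed and neither adds a bone-lesion condition.
- The literal reading would make the bone criterion in the PD row impossible to meet and would leave some patients in no category. An assessor is likely to notice, and the study chair reviews each suspected progression.
- The sentence that follows in Section 9, saying that imaging is not needed to satisfy the response requirements, suggests the clause was aimed at responses.
- TTP and PFS are secondary and descriptive in a single-arm trial. Section 10.4.2 names median PFS and median OS for reporting, not median TTP, which is the quantity illustrated above.
- The formula loses a random share of progressions. If bone progression tends to come earlier or later than other progression, the figures would differ.

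All of this stands as a limit on the consequence. It does not remove the contradiction. PD is named in Section 9, footnote a covers the whole table, and footnote c does not exempt PD from it. The plan relies on assessors and the study chair to guess which text prevails.

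**Conclusion.** The defect is an internal contradiction in the definition of progression. Section 9 and footnote a, as worded, require the absence of progressive or new bone lesions for PD itself; the PD row makes their presence sufficient. Depending on the text followed, a patient with known new lytic lesions is PD, SD by default, or unclassified.

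The effect on TTP and PFS is conditional. It is zero if the PD row is followed and upward if the general condition is followed, less for PFS than for TTP. Its size cannot be established from the documents: the 5.7 to 7.3 months rest on an assumed 10% to 30% share, an exponential model and a median borrowed from another study, and only patients imaged after baseline contribute. The response rate and the sample size are unaffected. Because the repair is small and the conflict is plain, it should be made.

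**What to change.** Split the Section 9 sentence in two. Keep the requirement of two consecutive assessments before new therapy for every category now listed, PD included. Then state separately that, for CR, sCR, VGPR and PR only, there must be no known progressive or new bone lesion where imaging was done, and that this second condition does not apply to PD. Narrow footnote a in the same way. Leave the PD row unchanged.

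MR needs no addition, because its row already carries its own bone condition. Dropping SD from footnote a opens no gap: a patient with definite new or enlarging lytic lesions meets the PD row and so falls outside SD by definition.

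The cost is one sentence in Section 9 and one in footnote a, with no new data or visits. If progressions with post-baseline imaging have already been classified, they should be re-read under the reconciled text before analysis. Reported TTP and PFS may come out slightly shorter.

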## 10. STATISTICAL CONSIDERATIONS AND DETERMINATION OF SAMPLE SIZE

### 10.1. Determination of Sample Size

MM 27 is a Phase I/Phase II study of carfilzomib in combination with panobinostat in the treatment of relapsed/refractory multiple myeloma. The total number of patients expected to be accrued is up to 80.

The Phase I efficacy objective is to establish the optimal dose of carfilzomib with panobinostat that can be administered to patients with relapsed/refractory multiple myeloma. In this part of the trial, the optimal dose combination to be administered will be determined as described in Section 5.2. Since 3-6 patients will be treated in each cohort, the maximum number of patients treated in this phase will be 24.

The Phase II efficacy objective is to evaluate the overall response in patients with relapsed/refractory multiple myeloma treated at the optimal dose level in the first 4 dose levels established during the Phase I portion. In addition, the overall response in patients at any additional dose levels will be evaluated. The response rates in the two dose levels will be evaluated separately. When used in the treatment of patients with relapsed/refractory multiple myeloma, the historical carfilzomib overall response rate is approximately 18%. It is hypothesized that the overall response rate for the treatment regimen of carfilzomib plus panobinostat is greater than that for patients treated with carfilzomib alone. A sample size of 27 achieves 80% power to detect an increase in the overall response rate to 36% (representing a 100% relative improvement) based on a one-sided test of proportion at an alpha level of 0.10. The sample size will be increased by 10% to account for potential non-evaluable patients and adjusted relative to the actual number of patients in the Phase I portion who are treated at the optimal dose level.

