## SYNOPSIS

Title of Study:	A Phase I/II Study of the Combination of Panobinostat and Carfilzomib in Patients with Relapsed/Refractory Multiple Myeloma	
Protocol Number:	MM 27	Study Phase: I-II
Study Centers:	Multicentered	
Objectives:	
Primary Objectives:
 
 
• To establish the optimal doses of carfilzomib in and panobinostat that can be administered to patients with relapsed/refractory multiple myeloma. (Phase I)
 
• To evaluate the overall response in patients with relapsed/refractory multiple myeloma treated with the combination of panobinostat and carfilzomib. (Phase II)
 
 
Secondary Objectives:
 
 
• To evaluate time-to-progression (TTP)
 
• To evaluate progression-free-survival (PFS)
 
• To evaluate overall-survival (OS)
 
• To evaluate safety
 
	
Study Design:	
This is an open-label, non-randomized Phase I/II study of patients with relapsed or refractory multiple myeloma.
 
The Phase I study will determine the MTD of the combination of carfilzomib and panobinostat. The Phase I portion will follow a standard dose escalation design, beginning with dose level 1 (see Table 2). Patients will be assessed for dose-limiting toxicity (DLT) at each visit during Cycle 1 prior to receiving treatment. Dose modifications will not be permitted during Cycle 1 unless a patient experiences a DLT (see Section 5.2.2.). Treatment cycles will be administered at 28-day intervals. Panobinostat will be administered orally three times weekly during weeks 1 and 3 of each cycle (Days 1, 3, 5, 15, 17, 19). Carfilzomib will be administered intravenously on Days 1, 2, 8, 9, 15, and 16 of each cycle. During Cycle 1, the carfilzomib dose will be escalated after the Day 2 dose, if well tolerated.
 
A maximum of four dose levels will be evaluated. Approximately 24 patients will be enrolled during the Phase I portion to establish the MTD.
 
In the Phase II portion of this study, patients with relapsed/refractory multiple myeloma will receive treatment with the panobinostat and carfilzomib combination established during Phase I. Patients will be reevaluated for response to treatment after each cycle (4 week). Patients with objective response or stable disease will continue treatment, with subsequent reevaluations every 4 weeks, until disease progression or unacceptable toxicity occurs.
	

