## SYNOPSIS

Drug Supply:
	
Panobinostat and Carfilzomib for use in the study will be provided to the Sponsor, SCRI Development Innovations, LLC (SCRI Innovations). Panobinostat will be provided to SCRI Innovations by Novartis Pharmaceuticals. Carfilzomib will be provided to SCRI Innovations by Onyx Pharmaceuticals. Supplies will be requested through SCRI Innovations.

Study Drug(s), Schedule, and Mode of Administration:
	
 
Relapsed/Refractory Multiple Myeloma Patient
 
↓
 
 
ENROLLED
 
 
↓
 
 
Phase I
 
N = 24
 
Panobinostat PO TBD TIW Days 1, 3, 5, 15, 17 and 19
 
Carfilzomib IV TBD Days 1, 2 escalating on Days 8, 9, 15, & 16
 
Dose to be determined
 
Treatment cycles will be repeated every 28 days
 
 
↓
 
 
Once the MTD has been determined, up to 30 patients with refractory/relapsed multiple myeloma may enroll in the Phase II portion.
 
 
↓
 
 
Phase II
 
Panobinostat PO TBD Days 1, 3, 5, 15, 17 and 19
 
Carfilzomib IV TBD Days 1, 2 escalating on Days 8, 9, 15, and 16
 
Treatment cycles will be repeated every 28 days
 
Restaging: patients will be restaged every treatment cycle (every 4 weeks). Patients with disease progression or unacceptable toxicity will be discontinued from the study.
 
 
↓
 
 
 
Continue until tumor progression, or until unacceptable toxicity occurs.
 
 
→
 
 
FOLLOW-UP
 
 
 

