**Table 3. Parallel Dose Escalation Study – Dose Levels 5 and 6**

28-Day Cycles	Cycle 1	Cycle 2 to Progression
Dose Level 5		
Carfilzomib	20 mg/m  IV D 1, 2 / 56 mg/m  IV D 8, 9, 15, 16	56 mg/m  IV D 1, 2, 8, 9, 15, 16
Panobinostat	30 mg D 1, 3, 5, 15, 17, 19	30 mg D 1, 3, 5, 15, 17, 19
Dose Level 6		
Carfilzomib	20 mg/m  IV D 1, 2 / 56 mg/m  IV D 8, 9, 15, 16	56 mg/m  IV D 1, 2, 8, 9, 15, 16
Panobinostat	20 mg D 1, 3, 5, 15, 17, 19	20 mg D 1, 3, 5, 15, 17, 19

A parallel Phase I study will occur to evaluate a minimum of 3 patients and a maximum of 6 patients following a standard dose escalation design at additional dose levels of the combination of carfilzomib and panobinostat.

Patients will enter in the dose level confirmed in their enrollment confirmation from SCRI Innovations.

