### **5.3. Phase II**

If a dose level in the parallel Phase I study is found to be tolerable, then additional patients will be recruited into an expansion cohort of 30 patients for Phase II for a total of 60 Phase II patients (including 30 patients for dose level 4).. A maximum of up to 80 total patients may be enrolled in this study (including patients from the dose escalation Phase I studies).

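### The enrolment figures in Section 10.1 and the synopsis were not updated for six dose levels and two expansions, and as printed they exceed the cap of 80

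*Combined protocol and SAP*

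**What the plan says.** Section 10.1, on Phase I, refers to Section 5.2 for how the dose is found. From 3 to 6 patients per cohort it concludes that "the maximum number of patients treated in this phase will be 24". The synopsis repeats the 24.

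Section 5.2 now has two dose tables. Table 2 holds levels 1 to 4 and a fallback level -1. Table 3 holds levels 5 and 6, with the text "A parallel Phase I study will occur to evaluate a minimum of 3 patients and a maximum of 6 patients". It is not clear whether the 3 to 6 applies to each level or to both together.

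The synopsis states "A maximum of four dose levels will be evaluated", and its schema says that "up to 30 patients with refractory/relapsed multiple myeloma may enroll in the Phase II portion". Section 5.3 instead plans 60 Phase II patients, 30 of them at level 4 and 30 at a tolerable additional level. It adds: "A maximum of up to 80 total patients may be enrolled in this study", and makes clear that Phase I patients count toward that number.

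Two other statements bear on how to add these up. Section 5 limits the additional level to 36 patients with its Phase I patients included. Section 10.1 says the expansion size is adjusted for Phase I patients already treated at the optimal dose.

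**The concern.** These are current planning figures in the operative statistics section and the synopsis. The 24 covers four levels, while the section it cites now describes six. The synopsis does not agree with itself: its parts give 24 + 30 = 54, yet it states a total of 80.

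Sites and ethics committees read the enrolment limit from these places. Section 13.1 lists an increase in subject number among the changes that need an amendment, so an unforeseen overrun has a procedural cost. The two dose levels are also evaluated separately for response, so it is fair to ask whether the cap could leave the second cohort below the size that the power statement requires.

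**Working it through.** **1. The plan's own sample size.** Inputs from Section 10.1: null rate 0.18 ("the historical carfilzomib overall response rate is approximately 18"%), alternative 0.36 ("to detect an increase in the overall response rate to 36"%), and the test ("based on a one-sided test of proportion at an alpha level of 0.10"). With n = 27, the exact binomial rule rejects at 8 or more responses:

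- P(X ≥ 8 | 27, 0.18) = 0.098, within 0.10
- P(X ≥ 8 | 27, 0.36) = 0.812

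This reproduces the stated 27 and 80%, and 27 is the smallest n with exact power of at least 0.80. Adding 10% gives 27 × 1.10 = 29.7, so 30 per cohort, as in Section 5.3.

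**2. The printed enrolment figures.** Phase I: 4 levels × 6 = 24. Phase II: 30 + 30 = 60. Sum: 24 + 60 = 84, which is above 80. If the 60 are additional to Phase I, the cap holds only when Phase I has at most 80 − 60 = 20 patients.

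**3. Totals on the documented path.** Section 5 says four levels were evaluated and no dose-limiting toxicity was seen. Under Section 5.2.1, a level with none among its first 3 patients escalates without adding more. Levels 1 to 4 therefore imply 4 × 3 = 12 patients, or 15 if level 4 was filled to 6 to meet the definition of the maximum tolerated dose in Section 5.2.3. The actual number is not given. I read the 3 to 6 in Table 3 as per level and assume that one additional level is expanded.

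| Reading | One additional level tested | Both tested |
|---|---|---|
| A. The 60 are additional to Phase I | 12 + 3 + 60 = 75 to 15 + 6 + 60 = 81 | 12 + 6 + 60 = 78 to 15 + 12 + 60 = 87 |
| B. Phase I patients at the expanded levels count within the 30s | 9 + 30 + 30 = 69 | 9 + 30 + (3 to 6) + 30 = 72 to 75 |
| B, with the additional level filled to 36 | 9 + 30 + 36 = 75 | 9 + 30 + (3 to 6) + 36 = 78 to 81 |

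Section 5 points to A, because 36 = 30 + 6. Section 10.1's adjustment points to B. If the 3 to 6 covers levels 5 and 6 together, the upper end under A is 12 + 6 + 60 = 78, or 15 + 6 + 60 = 81.

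**4. What the cap leaves for the second cohort.** Take both additional levels as tested, 6 patients at the one not expanded, and the second cohort's own Phase I patients counted in it:

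- A, 12 at levels 1 to 4: 80 − 12 − 30 − 6 = 32
- A, 15 at levels 1 to 4: 80 − 15 − 30 − 6 = 29
- B: 80 − 9 − 30 − 6 = 35

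Only 29 is below the planned 30, by one patient. With 10% non-evaluable, 29 × 0.9 = 26.1, so about 26 evaluable. The rule is then 8 or more of 26, with exact power 0.774.

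**5. Reading exact power at neighbouring sizes.** Exact power is 0.812 at n = 27, 0.729 at 28, 0.771 at 29, 0.840 at 31 and 0.769 at 32. It drops at 28 and at 32 because the number of responses required rises by one (8 to 9, then 9 to 10). A figure of 0.73 or 0.77 at n = 28, 29 or 32 therefore does not mean that patients are missing. The normal approximation, which has no such steps, gives 0.812 at 26 and 0.822 at 27.

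**The case against.** The best defence is that 24 is still correct for what it was written about. Section 5 separates the completed four-level portion from a parallel Phase I study with its own limit, and 24 bounds the first. In addition, 24, 36 and 80 are ceilings, and separate ceilings need not add to the overall cap. Both points have weight: 84 is not a forecast of enrolment, and under reading B the trial stays within 80 unless the additional level is filled to 36. They do not rescue the text. Section 10.1 applies 24 to the phase described in Section 5.2, which now includes levels 5 and 6. The synopsis figures of four levels and 30 patients contradict Section 5.3 on any reading. Nothing says whether A or B is meant.

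A reader might go further and infer that the second cohort is left seriously underpowered. Six patients at all six levels plus 60 would be 96. Under the cap that would leave 20 for the second cohort, with exact power of about 0.62. The documents do not support this. It needs 6 patients at every one of levels 1 to 4, whereas Section 5 reports no dose-limiting toxicity there and Section 5.2.1 then moves on after 3. It also gives level 4 no credit for its own Phase I patients, although Section 10.1 provides for that. Nor can level -1 be added to the count: Section 5.2.1 tests it only if level 1 exceeds the maximum tolerated dose, in which case the higher levels would not have been opened. Finally, no passage says that the last cohort would be the one cut.

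**Conclusion.** The point holds as an error in stated figures, of modest severity. The Phase I maximum in 10.1 and the synopsis is out of date, and the synopsis disagrees with Section 5.3 on dose levels and Phase II size. The printed 24 + 60 exceeds the cap by 4. On the documented path, whether the plan fits 80 depends on an unresolved conflict between Sections 5, 5.3 and 10.1: at most 7 over under reading A, and under reading B at most 1 over, and only if the additional level fills to 36.

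No material loss of power is shown, and the 27 and 80% are correct. The least favourable documented case is about 26 evaluable patients against 27.

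This rests on 3 patients at each of levels 1 to 4 (or 6 at level 4), 3 to 6 at each additional level tested, and one additional level expanded. Replacement of inevaluable Phase I patients, which Section 5.2.2 allows, would raise the totals.

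**What to change.** In Section 10.1 and the synopsis:

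- Replace 24 with the actual number treated at levels 1 to 4 plus the maximum for levels 5 and 6, and say whether 3 to 6 is per level or for both together.
- Replace the synopsis statements of four dose levels and up to 30 Phase II patients so that they match Section 5.3.
- State whether each 30 includes the Phase I patients treated at that level, and reconcile this with the 36 in Section 5.
- Give a per-level breakdown that adds to no more than 80.

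The cost is amendment wording only. No extra patients are needed and the power statement does not change.
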